### **4.3.3. Sensitivity Analyses**

#### **4.3.3.1. Two-Dimensional Tipping Point Analysis**

The two-dimensional tipping point analysis will be conducted for pivotal and all patients in the mITT with varying assumptions about the missing outcomes on the two treatment groups independently, including scenarios in which dropouts on setmelanotide group have worse outcomes than dropouts on placebo group. A penalty for the setmelanotide group and improvement on the placebo group will change by increments of 0.1 to 1, until the statistical significance is lost, i.e., until the p-value becomes  $>0.05$ .

### **4.3.4. Supplementary Analyses**

#### **4.3.4.1. Per-Protocol Population Analysis**

The primary analysis may also be repeated for the PP population for both pivotal patients and all patients. The per-protocol analysis will only be provided if the number of excluded patients in PP population is at least 10% of the overall mITT set.

#### **4.3.4.2. As-Observed Analysis**

The primary analysis will also be repeated for the mITT population for both pivotal and all patients based on observed data only.

#### **4.3.4.3. Last-Observation Carried Forward Analysis**

A last-observation-carried-forward (LOCF) analysis will be conducted for pivotal and all patients in the mITT. For any patients missing the primary timepoint BMI value, the last available BMI value occurring at an on-site visit (including unscheduled, additional, or early termination on-site visits) will be carried forward and used as the primary timepoint value for analysis purposes.

### **4.3.5. Key Secondary Efficacy Analyses**

Statistical testing will be performed on the key secondary endpoints according to the pre-specified hierarchical order as outlined in [Section 3.7](#). Formal inference of efficacy tests will be based on the pivotal patients and stop once a result showing no statistical significance in favor of the study drug at the 2-sided alpha level of 0.05 is achieved.

The key secondary endpoints will rely upon the imputed values utilized for the primary efficacy endpoint (BMI/BMI Z-Score) or rely upon newly imputed values following same methodology as the primary efficacy endpoint (weekly average in daily hunger) as outlined in [Section 3.10.3](#).

#### **4.3.5.1. Proportion of BMI/BMI Z-Score Percent Change from Baseline**

The proportion of patients with  $\geq 5\%$  reduction in BMI in adult patients ( $\geq 18$  years of age), or BMI Z-score reduction of  $\geq 0.2$  points in pediatric patients ( $< 18$  years of age) from baseline after approximately 52 weeks on a therapeutic regimen of setmelanotide compared to placebo will be analyzed for pivotal patients in the mITT.

The BMI Z-score will be calculated for patients aged 4 to <18. These calculations will utilize the World Health Organization's WHO 2007 BMI SAS Macro Package. This macro package includes source code, three permanent datasets containing WHO 2007 references as required for calculation, and a readme.pdf with instructions. The patient age, sex, and BMI will be provided into this macro and the resulting BMI Z-Score will be produced and pulled directly into the appropriate CDISC compliant dataset.

Similar to the handling outlined in [Section 3.10.1](#) if weight is collected but a corresponding height is not collected, the last available height record for that patient will be used in the calculation of BMI before this BMI is used as an input into the validated macro.

Analysis will be conducted using the following steps:

- Binomial proportions will be calculated for each treatment arm for each of the 100 imputed datasets. Analysis between arms will be conducted for each of the 100 imputed datasets with a Cochran-Mantel-Haenszel (CMH) test with adjustment of stratification factors of age group and subpopulation (Japanese and non-Japanese), as appropriate. For each MI dataset, the COMMONRISKDIFF option in PROC FREQ will calculate the adjusted estimate of the risk difference of success (setmelanotide minus placebo) over all strata with its 95% confidence interval (CI).
- The estimates of the risk difference and their standard errors for all the MI datasets will be input to PROC MIANALYZE.
- PROC MIANALYZE will output an overall estimate of the risk difference, its 95% CI, and a combined p-value.
- PROC MIANALYZE will also output overall estimates of the proportions of responders in each treatment arm, along with 95% CIs.

While formal hypothesis testing will be considered based on pivotal patients, this key secondary analysis will also be conducted for all patients.

This analysis will be repeated for the Japanese subpopulation to explore consistency of effect. Similarly to the primary endpoint, consistency will be claimed if the estimated treatment effect in the Japanese subpopulation is at least 50% of the observed, overall treatment effect in all patients.

This key secondary analysis will additionally be repeated for the PP population for pivotal patients only.

Descriptive statistics for the actual, change from baseline, and percent change from baseline in observed BMI Z-Score for patients <18 years of age will be provided by visit. Additional descriptive summaries will be provided for Japanese/non-Japanese subgroup for all patients, as needed.

Change from baseline in BMI Z-Score in observed values will be presented graphically by treatment group and visit, with standard error bars included, for the mITT for pivotal and all patients. The x-axis will include visit in weeks and the y-axis will represent the observed mean  $\pm$  SE of percent change from baseline.

A by-patient listing for BMI Z-Score observed values will be provided.

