## **7.5. Analysis of the Secondary Efficacy Endpoints**

### **7.5.1. Key Secondary Efficacy Endpoints**

Due to the rarity of the disease indication and small sample size, formal multiplicity adjustment procedures will not be enforced. However, to assist the comprehensive assessment and interpretation of the efficacy of setmelanotide, appropriate statistical testing will be performed on the key secondary efficacy endpoints according to the following hierarchical order to control the overall type I error rate. The p-values and the corresponding CIs will be provided.

- The proportion of patients with  $\geq 5\%$  reduction in BMI in adult patients ( $\geq 18$  years of age), or BMI Z-score reduction of  $\geq 0.2$  points in pediatric patients ( $< 18$  years of age) from Baseline after approximately 52 weeks on a therapeutic regimen of setmelanotide compared to placebo.

The between-group comparison on the proportion of patients with  $\geq 5\%$  reduction in BMI in adult patients ( $\geq 18$  years of age), or BMI Z-score reduction of  $\geq 0.2$  in pediatric patients ( $< 18$  years of age) from Baseline after approximately 52 weeks on a therapeutic regimen will be conducted with a Cochran–Mantel–Haenszel (CMH) test with adjustment of stratification factors of age group and subpopulation (Japanese

and non-Japanese). The associated corresponding 2-sided 95% CI will be presented. The analysis will be based on the mITT.

- The proportion of all patients with  $\geq 5\%$  reduction in BMI from baseline after approximately 52 weeks on a therapeutic regimen of setmelanotide compared to placebo.

The between-group comparison on the proportion of all patients with  $\geq 5\%$  reduction in BMI from baseline after approximately 52 weeks on a therapeutic regimen will be conducted Cochran–Mantel–Haenszel (CMH) test with adjustment of stratification factors of age group and subpopulation (Japanese and non-Japanese) at a 2-sided 0.05 significance level. The associated corresponding 2-sided 95% CI will be presented. The analysis will be based on the mITT.

- Mean change in the weekly average of the daily most hunger score in patients  $\geq 12$  years old from Baseline after approximately 52 weeks on a therapeutic regimen of setmelanotide compared to placebo.

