### 3. GENERAL STATISTICAL METHODS

#### 3.1. Sample Size Justification

The sample size is mainly driven by the primary efficacy hypothesis with the safety database taken into consideration. With the planned sample size of ~120 patients (~80 patients in setmelanotide group vs ~40 patients in placebo group), the trial provides ~99.5% power to detect a treatment difference (treatment - placebo) of -10% in percent change of BMI from baseline after approximately 52 weeks on a therapeutic regimen of setmelanotide at 2-sided alpha of 0.05, assuming a common standard deviation of 10% (estimated from trial RM-493-030), a dropout rate of 20%, and 2:1 randomization.

It is planned to enroll ~12 patients from Japan within the ~120 patients. Using the Method 1 described in PMDA guidance, simulation studies (nsim = 100000 runs) confirmed that the sample size of 12 Japanese patients will provide 80.1% probability that  $D_{\text{Japan}}/D_{\text{all}} > 0.5$  (D: Difference between study drug and placebo for the primary endpoint).

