#### **4.3.5.2. Proportion of All Patients with $\geq 5\%$ Reduction in BMI from Baseline**

The proportion of pivotal patients with  $\geq 5\%$  reduction in BMI from baseline after approximately 52 weeks on a therapeutic regimen of setmelanotide compared to placebo will be analyzed following the same methodology described in [Section 4.3.5.1](#) above for the mITT.

Similar to the above, formal analysis will be conducted based on pivotal patients, but the analysis will be repeated for all patients.

This analysis will also be repeated for the Japanese subpopulation to explore consistency of effect. Similarly to the primary endpoint, consistency will be claimed if the estimated treatment effect in the Japanese subpopulation is at least 50% of the observed, overall treatment effect in all patients.

This key secondary analysis will additionally be repeated for the PP population for pivotal patients only.

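### The two responder key secondary endpoints are assigned a CMH test, but their p-value comes from a Wald-type test on the pooled risk difference, which at 2:1 allocation and low-to-moderate response rates is too liberal in favour of setmelanotide

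*SAP*

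**What the plan says.** Protocol 7.5.1 assigns the responder key secondary endpoints a "Cochran–Mantel–Haenszel (CMH) test with adjustment of stratification factors of age group and subpopulation (Japanese and non-Japanese) at a 2-sided 0.05 significance level". The first analysis bullet of SAP 4.3.5.1 repeats the CMH test, to be run in each of the 100 imputed datasets, and asks PROC FREQ for a common risk difference alongside it.

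The pooling bullets then leave the CMH result behind: "The estimates of the risk difference and their standard errors for all the MI datasets will be input to PROC MIANALYZE". After that, "PROC MIANALYZE will output an overall estimate of the risk difference, its 95% CI, and a combined p-value". SAP 4.3.5.2 handles the second responder endpoint "following the same methodology described in" 4.3.5.1. Sections 4.3.6.1, 4.3.6.3, 4.3.6.4, 4.3.6.7 and 4.3.6.8 refer back to the same method.

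Under SAP 4.3.5, formal testing stops at the first result showing "no statistical significance in favor of the study drug at the 2-sided alpha level of 0.05 is achieved". These p-values therefore decide key secondary endpoints 1 and 2, and whether the hunger endpoint may be tested.

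**The concern.** The plan names one test and computes another. A CMH test takes its variance under the null hypothesis. A risk difference divided by its own standard error takes its variance from the two observed proportions. With equal arms the difference is small and symmetric between directions. With twice as many patients on setmelanotide it is not symmetric. The placebo arm contributes most of the variance, and when few placebo patients respond by chance, the estimated placebo variance falls just as the apparent benefit grows.

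At stake is the error rate of the first two steps of the fixed sequence in the direction that supports a claim. The sponsor also could not say from the text which p-value governs if the two disagree.

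**Working it through.** **1. Tracing the p-value.** Only two quantities per imputed dataset reach the pooling step: the common risk difference and its standard error. No step passes on a CMH chi-square or a transform of it. The combined p-value is therefore the pooled estimate divided by its Rubin standard error. One hundred CMH tests are run and none is used.

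**2. Inputs.** From SAP 3.1: about 80 versus 40 patients, and "assuming a common standard deviation of 10% (estimated from trial RM-493-030), a dropout rate of 20%, and 2:1 randomization". From SAP 4.3.5: two-sided 0.05, so 2.5% in the setmelanotide tail. The plan's own power figure reproduces. With 64 versus 32 after dropout, the standard error is 10 × √(1/64 + 1/32) = 2.165, the noncentrality is 10/2.165 = 4.62 on 94 degrees of freedom, and power is 99.55% (stated: about 99.5%). That figure concerns the primary endpoint. No power, error rate or response rate is given for the responder endpoints.

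**3. Assumed null response rates.** If percent BMI change is normal with SD 10% and mean m, P(reduction ≥5%) = Φ((−5 − m)/10). For assumed m = 0, +3 and +5 this is Φ(−0.5) = 31%, Φ(−0.8) = 21% and Φ(−1.0) = 16%. I add 10% as a lower case. This covers the ≥5% BMI criterion only; nothing in the documents gives a null rate for the pediatric Z-score criterion.

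**4. A split decision.** Take 20/80 versus 4/40 in one stratum, a difference of 0.15.
- Wald: variance 0.25 × 0.75/80 + 0.10 × 0.90/40 = 0.00459; z = 0.15/0.0678 = 2.21; p = 0.027.
- CMH: pooled rate 24/120 = 0.20; variance 0.20 × 0.80 × (1/80 + 1/40) × 120/119 = 0.00605; z = 0.15/0.0778 = 1.93; p = 0.054.

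**5. Exact error rates.** These come from full binomial enumeration at 80:40 with one stratum, complete data and equal true rates. In one stratum the Sato variance of the Mantel-Haenszel risk difference equals the unpooled variance used here.

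| Common rate | Wald, setmelanotide tail | Wald, placebo tail | CMH, setmelanotide tail |
|---|---|---|---|
| 10% | 5.0% | 1.5% | 1.7% |
| 16% | 4.1% | 2.0% | 2.0% |
| 21% | 3.8% | 2.2% | 2.2% |
| 31% | 3.3% | 2.4% | 2.4% |
| 50% | 3.1% | 3.1% | 2.3% |
| 65% | 2.6% | 3.1% | 2.6% |
| 70% | 2.4% | 3.3% | 2.6% |

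A simulation with six assumed strata (one million trials, Mantel-Haenszel weights, Sato variance) gives 5.0%, 3.8% and 3.4% at 10%, 20% and 30%. At 60:60 and a 20% rate the Wald tails are equal, at 2.7% each. The asymmetry therefore needs unequal allocation together with a rate away from 50%.

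**6. With multiple imputation.** Setmelanotide tail of the Wald test after Rubin pooling, 100 imputations. Assumptions: normal within-arm imputation, correlation 0.7 with an interim value, simulation error about 0.2 points.

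| Missing | 10% rate | 20% rate | 30–31% rate |
|---|---|---|---|
| 5% | 4.6% | 3.7% | 3.4% |
| 10% | 4.4% | 3.5% | 2.9% |
| 20% | 3.6% | 2.8% | 2.4% |

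At 20% missing the two-sided level is 4.2% to 4.6%, and the pooled CMH version gives 1.2% to 1.6% in the setmelanotide tail over these rates. Imputing responder status directly, which the SAP does not do, leaves a larger excess at 20% missing (3.5% to 4.4%). Under wash-out imputation the Wald figure is 1.6% to 2.4% at rates of about 16% and above, and 3.4% at 10%.

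**7. With the gate on the primary endpoint.** If both arms share the same distribution of BMI change, the primary null is also true, so reaching and rejecting the responder test cannot exceed 2.5%. Simulated, it is 1.2%, 1.1% and 1.0% at 31%, 21% and 16%. If the mean BMI effect is real but responder proportions are equal, the gate removes little: 3.3% to 4.1% for Wald against 2.0% to 2.4% for CMH.

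**The case against.** The strongest reply is that the mismatch is one of labelling with little practical effect. Much of that stands.

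- **Gating.** A reader might infer that the step-down fails to control type I error in general. It does not fail under the global null (step 7). The excess needs a true mean effect with equal responder proportions. That is a narrower case, but it is the one a fixed sequence must protect once the primary has succeeded.
- **Direction.** A reader might infer that 2:1 allocation by itself makes the test favour setmelanotide. It does not: the tails are equal at a 50% rate, and the setmelanotide tail is conservative above roughly 65% to 70%. The low-to-moderate range is an assumption. Protocol 2.1, which describes the weight gain as largely resistant to treatment, makes it reasonable but gives no rate.
- **Missing data.** At the plan's 20%, pooling removes much of the excess and the two-sided level is below 5%. But the 20% is a dropout rate, and Protocol 4.3 asks patients who stop treatment to stay for assessments, so the missing fraction may be lower and the excess larger.
- **Planned effect.** At 31% versus 69% down to 16% versus 50%, power is 97% to 99% at 80:40 and 93% to 96% at 64:32. The two tests then differ in only 0.4% to 0.6% of trials at 80:40 and 0.1% to 2.2% at 64:32.
- **Declared change.** Protocol 7 lets the SAP modify the methods, and the SAP's list of changes is redacted, so the documents do not support calling this an undeclared departure. The current SAP text still names CMH, however.

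**Conclusion.** The inconsistency is certain: CMH is the named test, and a Wald-type test on the common risk difference supplies the p-value. Its consequence is conditional. At 80:40, complete data and an assumed common response rate of 10% to 31%, the setmelanotide tail is 5.0% down to 3.3% instead of 2.5%, against 1.7% to 2.4% for CMH. At 20% missing with continuous imputation it is about 2.4% to 3.6%. Under wash-out it is largely gone at rates of about 16% and above.

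The multi-stratum figures assume Mantel-Haenszel weights with the Sato variance, because the SAP names neither; that omission is a gap in itself. A large effect would be detected by either test. The point matters for a borderline result, where the plan as written could yield a claim that its named test would not. It should be corrected before unblinding, but it does not undermine the primary analysis.

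**What to change.** In SAP 4.3.5.1, take the step-down p-value from the signed standardised CMH statistic. In each imputed dataset compute Z = (observed minus expected setmelanotide responders, summed over strata) / √(summed hypergeometric variances). Pass the 100 values of Z to PROC MIANALYZE with within-imputation variance 1, giving total variance 1 + (1 + 1/100)B, where B is the between-imputation variance. Keep the sign: pooling a transformed, unsigned chi-square would lose the direction that SAP 4.3.5 requires.

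Keep the stratified risk difference and its CI as the estimate, and name its weights and variance estimator. State that the CMH p-value governs the sequence. Carry the change to 4.3.5.2 and to 4.3.6.1, 4.3.6.3, 4.3.6.4, 4.3.6.7 and 4.3.6.8.

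The cost is a few lines of SAP text and code, slightly larger p-values, and some conservatism at low response rates. The p-value and CI may also disagree in borderline cases, which the SAP should acknowledge because Protocol 7.5.1 presents the two together. Simply relabelling the test as Wald and naming its variance would remove the contradiction but leave the error rate as it is.

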#### **4.3.5.2. Proportion of All Patients with $\geq 5\%$ Reduction in BMI from Baseline**

The proportion of pivotal patients with  $\geq 5\%$  reduction in BMI from baseline after approximately 52 weeks on a therapeutic regimen of setmelanotide compared to placebo will be analyzed following the same methodology described in [Section 4.3.5.1](#) above for the mITT.

Similar to the above, formal analysis will be conducted based on pivotal patients, but the analysis will be repeated for all patients.

This analysis will also be repeated for the Japanese subpopulation to explore consistency of effect. Similarly to the primary endpoint, consistency will be claimed if the estimated treatment effect in the Japanese subpopulation is at least 50% of the observed, overall treatment effect in all patients.

This key secondary analysis will additionally be repeated for the PP population for pivotal patients only.

#### **4.3.5.3. Daily Hunger Questionnaire Change from Baseline**

Mean change from baseline in the weekly average of the daily hunger scores for pivotal patients  $\geq 12$  years old in the mITT after 52 weeks on therapeutic regimen will be analyzed to compare setmelanotide versus placebo.

Analysis will be conducted with an ANCOVA model, assuming unequal variance to account for possible unequal residual variances and adjusted with baseline weekly average of daily most hunger score and stratification factors of age group ( $\geq 18$  years old,  $\geq 12$  and  $< 18$  years old) and subpopulations (Japanese and non-Japanese), as appropriate. The ANCOVA model will be run for each of the 100 imputed datasets (according to [Section 3.10.3](#)) and the outcomes from each of the 100 imputed datasets will be combined using Rubin's Rule to provide an overall estimate against the null hypothesis with corresponding confidence intervals and p-value.

Daily hunger questionnaire scores are recorded for 7 consecutive days before each scheduled trial visit.

Prior to analysis, daily hunger scores for each of the hunger assessments will be averaged separately for the 7 days immediately preceding the visit. The hunger score on the day of the visit will not be considered as prior to visit and thus the daily scores over the 7 days prior to, and not considering day of visit, will be considered. Only if all 7 days prior to randomization (baseline) are missing, will we consider the day of visit (Day 1). This will help to ensure non-missing baseline values for this key secondary endpoint.

Once these daily scores are identified, the weekly average of daily scores will be equal to the average of the daily scores over the 7 identified days. For a week of hunger scores to be considered evaluable, scores need to be recorded and available for analysis on at least 1 of 7 days to provide sufficient data to determine mean values. Unless specified otherwise, this will be applicable for all daily hunger score related analyses.

While formal hypothesis testing will be considered based on pivotal patients, the analysis will also be conducted for all patients.

This analysis will also be repeated for the Japanese subpopulation to explore consistency of effect. Similarly to the primary endpoint, consistency will be claimed if the estimated treatment effect in the Japanese subpopulation is at least 50% of the observed, overall treatment effect in all patients.

This key secondary analysis will additionally be repeated for the PP population for pivotal patients only.

The actual and change from baseline for observed values of weekly average of daily hunger scores will be summarized descriptively by visit for pivotal and all patients for the mITT, as needed. Additional descriptive summaries will be provided for the Japanese/non-Japanese subgroup for all patients, as needed.

Change from baseline in weekly average of daily hunger scores observed values will be presented graphically by treatment group and visit, with standard error bars included, for the mITT for pivotal and all patients. The x-axis will include visit in weeks and the y-axis will represent the observed mean  $\pm$  SE of change from baseline.

A by-patient listing for observed hunger score responses will be provided.

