
### 4.3.2. Primary Efficacy Analysis

The primary efficacy endpoint of this study is the mean percent change from baseline in BMI after 52 weeks of treatment with the therapeutic regimen of either setmelanotide or placebo.

The statistical hypothesis for the primary efficacy endpoint is:

$$H_0: \mu_t - \mu_p \geq 0 \text{ vs } H_1: \mu_t - \mu_p < 0$$

where  $\mu_t$  is the mean percent change in BMI from baseline after approximately 52 weeks on a therapeutic regimen in setmelanotide group, and  $\mu_p$  is the mean percent change in BMI from baseline after approximately 52 weeks in placebo group.

The primary endpoint will be conducted on the mITT utilizing BMI values resultant from the multiple imputation process as outlined in [Section 3.10.2](#). The difference between setmelanotide and placebo after 52 weeks on therapeutic dose will be estimated using an ANCOVA model with unequal variance to account for possible unequal residual variances. The model will be adjusted with stratification factors of age group ( $\geq 18$  years old,  $\geq 12$  and  $< 18$  years old, and  $< 12$  years old) and subpopulation (Japanese and non-Japanese) as appropriate. This difference will be estimated for each of the 100 imputed datasets. The outcomes from the 100 imputed datasets will be combined using Rubin's Rule ([Little and Rubin, 2002](#)) through SAS PROC MIANALYZE to provide an overall estimate of least squares (LS) mean difference with corresponding 95% confidence intervals (CI) and p-value. The success criterion for the primary hypothesis requires the rejection of the null hypothesis at the 2-sided 0.05 significance level.

While formal hypothesis testing will be considered based on pivotal patients, the primary analysis will also be conducted for all patients.

The primary analysis will be repeated for Japanese patients to explore consistency of effect for the PMDA. Consistency will be determined as an observed treatment effect in Japanese patients of at least 50% of the observed, overall treatment effect (seen in all patients), in alignment with PMDA Method 1. All patients are the basis for comparison as this is the set of patients that consists of all 12 Japanese patients.

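### The Japanese consistency rule sets no condition on the all-patient effect, so followed literally it can declare consistency for an endpoint with no overall benefit

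*SAP*

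**What the plan says.** SAP 3.1 introduces the criterion as a ratio, D_Japan/D_all > 0.5, with "D: Difference between study drug and placebo for the primary endpoint". It reports that "simulation studies (nsim = 100000 runs) confirmed that the sample size of 12 Japanese patients will provide 80.1% probability that" this ratio is exceeded.

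SAP 4.3.2 applies the rule to the primary endpoint: "Consistency will be determined as an observed treatment effect in Japanese patients of at least 50% of the observed, overall treatment effect", with all patients as the reference set and PMDA Method 1 as the stated basis. SAP 4.3.5.1, 4.3.5.2 and 4.3.5.3 extend it to the three key secondary endpoints. In each, "consistency will be claimed if the estimated treatment effect in the Japanese subpopulation is at least 50% of the observed, overall treatment effect".

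The nearest text to a precondition is in SAP 4.3.5: "Formal inference of efficacy tests will be based on the pivotal patients and stop once a result showing no statistical significance" in favour of the drug is reached. That sentence governs formal tests in the pivotal cohort. It does not mention the consistency rule, which is computed on all patients.

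SAP 3.12.1 bases the trial's success or failure on the pivotal cohort alone and treats the Japanese evaluations as supportive and exploratory, outside the core package except for a PMDA submission.

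**The concern.** The rule takes two inputs, the Japanese estimate and the all-patient estimate, and compares one with half of the other. It does not look at the sign or the precision of the all-patient estimate. If that estimate is noise around zero, the rule compares noise with noise. Because the Japanese patients are also part of the all-patient set, the ratio is centred on 1, so it passes 0.5 easily. If both estimates favour placebo, the ratio is positive and can still pass.

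This matters little for the primary endpoint, where the planned power is about 99.5%. It matters more for the key secondary endpoints, for which the SAP gives no effect size, SD or power. Hunger is tested last and only in patients aged 12 or over. If the primary succeeds and hunger does not, the SAP as written could still call for a statement, usable in a PMDA submission, that the hunger effect in Japanese patients is consistent with an overall effect that was not shown.

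**Working it through.** **Inputs.** All from SAP 3.1: 80 versus 40 patients, 12 of them Japanese (share f = 12/120 = 0.10), SD 10, difference −10, two-sided alpha 0.05. Assumptions: normal estimates, equal variances, and 2:1 allocation within the Japanese subset (8:4). Below, positive means favourable to setmelanotide.

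**1. Reproduce the plan's 80.1%.** The variance of D_all is s² = 10² × (1/80 + 1/40) = 3.75. The variance of D_Japan is s²/f, and the covariance of the two is s². So

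Var(D_Japan − 0.5·D_all) = s²(1/f − 1 + 0.25) = 3.75 × 9.25 = 34.69, with square root 5.89.

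P = Φ(0.5 × 10 / 5.89) = Φ(0.849) = 80.2%. With 12 Japanese patients among 132 it is 80.1%. The SAP figure reproduces, so this is the rule the sponsor evaluated.

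**2. No effect anywhere, ratio reading.** Write D_Japan/D_all = 1 + (D_Japan − D_all)/D_all. Numerator and denominator of the last term are independent, with variances s²(1/f − 1) = 9s² and s². The ratio is therefore Cauchy with centre 1 and scale 3, and

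P(ratio ≥ 0.5) = 0.5 + arctan(0.5/3)/π = 0.5 + 0.1651/3.1416 = 55.3%.

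By symmetry half of this, 27.6 points, arises with both estimates favouring placebo. SD cancels, so the result carries over to hunger given the Japanese share. At 12 of 132 it is 55.0%. The Japanese share among patients aged 12 or over is not given; an assumed range of 0.05 to 0.20 gives 53.6% to 57.8%.

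**3. No effect anywhere, signed-inequality reading.** If the rule means D_Japan ≥ 0.5·D_all in the favourable direction, D_Japan − 0.5·D_all is normal with mean 0 and the probability is 50%.

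**4. Responder endpoints.** Simulation with a common response rate of 10% to 30%, Japanese 8:4 and others 80:40, gives 40% to 49% on the ratio reading and 52% to 56% on the inequality reading. Zero Japanese differences drive the gap: at a 10% rate, the chance of no responder among 12 patients is 0.9^12 = 28%.

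**5. Small true effects (simulation, continuous endpoint).** With a true −2 the ratio rule is met 58% of the time, while the overall result is significant in 18%. With true harm of +2 it is met 58% of the time on the ratio reading and 43% on the inequality reading.

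**6. Effect of adding conditions (simulation, f = 0.10).**

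| Scenario | As written (ratio) | Favourable direction required | 95% CI excluding 0 also required |
|---|---|---|---|
| No effect | 55.3% | 27.6% | 1.6% |
| Planned −10 | 80.2% | 80.2% | 80.2% |
| Endpoint with 80% power | 67.7% | 67.6% | 55.9% |
| Endpoint with 50% power | 62.8% | 61.5% | 33.8% |

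**7. Japan truly different.** With Japan 0 and others −10, the mean of D_all is 0.9 × 10 = 9 and P = Φ(−4.5/5.89) = Φ(−0.764) = 22.2%. Requiring the CI to exclude 0 leaves this at about 22%, because the all-patient result is almost always significant in that scenario.

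**The case against.** The strongest reply is that 55% is not an error rate. If the drug does nothing in either group, the two effects are equal and calling them consistent is, in a sense, true. This stands. A reader might take the 55% as a false-positive rate; it is only the frequency with which the label appears when there is no benefit to be consistent with.

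Second, the consequence is limited. Trial success rests on the pivotal cohort, the Japanese analysis is exploratory, and with no effect anywhere the primary test would nearly always fail. The case that matters is a positive primary with a null key secondary endpoint, and the documents give no likelihood for it. This also stands.

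Third, the label would not appear alone. The all-patient analyses yield estimates, 95% CIs and p-values, repeating them in Japanese patients gives the same outputs, and protocol 7.4 adds an interaction assessment for the primary endpoint. A null overall result would be visible. That softens the point but does not answer it: the SAP still says that consistency will be claimed, and a prespecified rule should not depend on unstated restraint.

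Fourth, the figures depend on the reading. The explicit ratio appears only in SAP 3.1, for the primary endpoint; the later sections can be read as a signed inequality. That two readings give different answers under harm is itself a reason to state the direction.

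Finally, the rule cites PMDA Method 1. Whether that guidance already presupposes an overall effect cannot be checked from these documents. The SAP's own wording does not say so.

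**Conclusion.** The gap is real and modest. As written, the rule can produce a consistency claim for an endpoint with no overall benefit or with harm: about 55% of the time under no effect on the ratio reading, 50% on the inequality reading, and roughly 40% to 56% for responder endpoints. The continuous figures assume normal estimates, equal variances, 2:1 allocation within strata and a Japanese share near 10%. The responder figures also assume a common response rate of 10% to 30%.

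Three stronger readings are not supported. The no-effect figure does not exceed one half for every endpoint: on the ratio reading the responder endpoints fall below it. The rule does not put the trial's formal conclusion at risk. And conditioning on the overall result would not make the rule better at detecting a truly different Japanese effect; about 22% false consistency remains when Japan is 0 and others are −10.

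**What to change.** In SAP 4.3.2 and 4.3.5.1 to 4.3.5.3, state that consistency is claimed for an endpoint only if the all-patient estimate favours setmelanotide (negative for BMI change and hunger, positive for responder differences) and the Japanese estimate is in the same direction and at least 50% of it. Add that where the all-patient 95% CI does not exclude 0, the ratio is reported descriptively beside the Japanese estimate and its 95% CI, with no claim of consistent benefit. Say also that this CI condition is a reporting rule on the all-patient set and does not reopen the pivotal-cohort hierarchy.

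The cost is a short addition to four sections, with no new data or patients. The direction condition loses almost nothing (67.7% to 67.6% at 80% endpoint power, 62.8% to 61.5% at 50%). Withholding the claim when the CI includes 0 is free at the planned primary effect but has a price elsewhere: correct claims fall from about 68% to 56% for an endpoint with 80% power and from about 63% to 34% at 50% power. The sponsor should accept that loss knowingly, since the SAP states no power for the key secondary endpoints.
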